11.4.6.2 Primary Analysis: QTcF Effect

The primary hypothesis to be tested is that following administration of zoliflodacin 2 g and 4 g, the upper bound of the one-sided 95% CI of treatment effect on $\Delta\Delta\text{QTcF}$ is ≥ 10 msec for at least one of the ECG assessments, against the alternative hypothesis that all mean effects are < 10 msec.

The primary analyses will be conducted to evaluate the effects of zoliflodacin 2 g and 4 g on cardiac repolarization as measured by ΔQTcF relative to placebo. Analysis will be performed using a linear mixed model with $\Delta\Delta\text{QTcF}$ as the dependent variable, with baseline QTcF, sequence, period, treatment, time (categorical), and interactions of time with treatment as fixed

effects, and subject nested within sequence as random effects. At each of the 9 post-baseline timepoints and for each zoliflodacin dose, a one-sided 95% CI for the treatment effect on $\Delta\Delta\text{QTcF}$ will be estimated using least square means. There will be 18 CIs, one for each combination of zoliflodacin dose and timepoint. A negative effect of 2 g or 4 g zoliflodacin will be concluded if the maximum of the 18 one-sided 95% CI upper bound is <10 msec. No adjustment will be made for multiplicity, since it is not required under intersection-union testing, as planned for the trial. No subgroup analyses are planned.

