Regulatory guidance has emphasized the need to obtain clear robust data on the effect of new chemical entities on ECG parameters with focus on cardiac repolarization as measured by the corrected QT interval (QTc) duration.¹⁶ Though many Phase 1, 2, and 3 studies may be conducted, they usually have insufficient sample size, infrequent sampling of ECG data, or the use of inadequate controls to overcome the high rate of spontaneous change in QTc duration.

This has resulted in regulatory guidance recommending a dedicated TQT study to define the ECG effects of new drugs.¹⁶

Therefore, this four-arm crossover trial will include therapeutic and suprathreshold dosing with zoliflodacin, placebo as a negative control, and oral moxifloxacin as a positive control. The trial will be conducted in accordance with relevant ICH E14 and Food and Drug Administration (FDA) guidance.¹⁶

The positive control (moxifloxacin) will serve to validate the sensitivity of the assay to detect small increases from baseline in the QTc interval corrected using Fridericia's formula (QTcF). Moxifloxacin will be used because it has been demonstrated to increase QTc by a mean of 6 msec (time-averaged analysis: standard deviation (SD) = 26 msec; N = 787) after a 400-mg oral dose.^{16,18} However, thorough ECG studies have shown that this dose of moxifloxacin can be expected to show, for a time-matched analysis, a mean change of 10-15 msec, generally within 1-6 h after dosing.¹⁹

This trial will be performed in healthy subjects to eliminate variables known to change ECG parameters (e.g., concomitant drugs or diseases) among subjects. The sample size is driven by the need to do a time-matched statistical analysis on the primary endpoint as per ICH E14 guidance. A crossover study design was chosen so that subjects will act as their own controls. A crossover trial can be conducted since the half-life of zoliflodacin is approximately 6 h. A wash-out phase of 8 ±2 days after Day 1 of each dosing period is considered sufficient to prevent a carryover effect of the study drug between treatments.

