11.4.6.4 Assay Sensitivity

Another secondary hypothesis is that a moderate increase in QTcF with administration of the positive control moxifloxacin 400 mg is detectable in this trial.

The model as described in the primary analyses will be repeated with the moxifloxacin treatment for assay sensitivity evaluation. The 1, 2, 3, and 4 h timepoints will be evaluated for assay sensitivity. Type I error (familywise error rate) will be controlled at an overall level of 5% by using a prespecified multiplicity adjustment. Assay sensitivity will be demonstrated if the lower bound of one-sided 95% CI (bounds will vary based on multiplicity adjustment) for treatment effect on $\Delta\Delta\text{QTcF}$ in at least one timepoint is >5 msec. In addition, two-sided 90% CIs will be obtained for the treatment effect on $\Delta\Delta\text{QTcF}$ at every timepoint and displayed graphically.

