5.4. Analysis of Central Tendency (By-timepoint Analysis)

By-timepoint analysis will be performed using Holter ECG data from subjects in the Holter ECG Analysis Population. Absolute values, change-from-baseline and time-matched, placebo-corrected, change-from-baseline values for each ECG parameter will be considered for this analysis (Refer to DMID 16-0110_ECG_Table shells: Tables 3, 4 and 5; DMID 16-0110_ECG_Listing shells: Listings 1 to 7; DMID 16-0110_ECG_Figure shells: Figure 1 to 56). Change-from-baseline QTcF (Δ QTcF) values (and other ECG parameters QTcB, HR

[calculated from RR], RR, QT, PR and QRS duration values) will be calculated by subtracting the mean value of replicate ECGs at baseline from the mean value of replicate ECGs at post-dose timepoints.

Time-matched, placebo-corrected, change from baseline in QTcF interval ($\Delta\Delta\text{QTcF}$) values (and other ECG parameters QTcB, HR [calculated from RR], RR, QT, PR and QRS duration values) will be calculated as differences between time-matched change-from-baseline QTcF values for active treatment minus time-matched change-from-baseline QTcF values for placebo for each subject (Refer to DMID 16-0110_ECG_Table shells: Table 5; DMID 16-0110_ECG_Listing shells: Listings 1 to 7).

As a primary analysis, a repeated measurement analysis on $\Delta\Delta\text{QTcF}$ values will be performed at each post-dose timepoint using analysis of covariance (ANCOVA) (Refer to DMID 16-0110_ECG_Table shells: Table 6; DMID 16-0110_ECG_Figure shells: Figure 57). Unless otherwise specified, a restricted maximum likelihood based, linear mixed effect model will be used. Model will include $\Delta\Delta\text{QTcF}$ as the dependent variable. Baseline QTcF value as continuous covariate and sequence, period, treatment, nominal timepoint (as categorical) and interactions of timepoint with treatment will be treated as fixed effects. The model will also include subject nested within sequence as a random effect. SAS PROC MIXED will be used to perform the analysis.

At each of the 9 post-dose timepoints and for each zoliflodacin dose, a one-sided 95% CI for the treatment effect on $\Delta\Delta\text{QTcF}$ will be estimated using least square (LS) means. There will be 18 CIs, one for each combination of zoliflodacin dose and timepoint. A negative effect of 2 g or 4 g zoliflodacin will be concluded if the maximum of the 18 one-sided 95% CI upper bounds is <10 msec. No adjustment will be made for multiplicity.

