SAS code will be similar to:

```
PROC MIXED;
  CLASS TREATMENT PERIOD SEQUENCE TIME SUBJ;
  MODEL   $\Delta\Delta\text{QTcF}$  = TREATMENT PERIOD SEQUENCE TIME BASELINE_QTCF
  TIME*TREATMENT;
  RANDOM SUBJECT(SEQUENCE);
  REPEATED TIME / SUBJ=SUBJ(PERIOD) TYPE=CS;
  LSMEANS TIME*TREATMENT / ALPHA=0.1;
RUN;
```

In the above model, treatment will be Zoliflodacin 2 g and Zoliflodacin 4 g.

Similar ANCOVA models will also be done for QTcB, HR (calculated from RR), RR, QT, PR and QRS as secondary analyses (Refer to DMID 16-0110_ECG_Table shells: Table 6; DMID 16-0110_ECG_Figure shells: Figure 57 to 63).

The analysis will also be presented in graphs. For each of the 2 active treatments, all 9 confidence intervals (corresponding to the 9 post-dose timepoints) will be presented on one graph. The change from baseline (ΔQTcF) and placebo-corrected change from baseline QTcF ($\Delta\Delta\text{QTcF}$) will be presented separately (Refer to DMID 16-0110_ECG_Figure shells: Figure 57 to 63).

Assay sensitivity (i.e., the ability to detect small increases from baseline QTcF duration) will be established by comparing the time-matched placebo-corrected change from baseline in QTcF in the moxifloxacin at the following 4 timepoints, i.e., 1, 2, 3, and 4 hours post-dose. The model as described in the primary analyses will be used. If the lower bound of one-sided 95% CI for treatment effect on $\Delta\Delta\text{QTcF}$ in at least one timepoint is >5 msec, it will be concluded that the assay is sensitive to small increases in baseline QTcF duration. Multiplicity adjustment will be done using the Bonferroni correction method. Since 4 timepoints and overall two-sided alpha of 0.1 are included in the analysis, two-sided alpha will be set to $0.1/4 = 0.025$ in the model (Refer to DMID 16-0110_ECG_Figure shells: Figures 64 and 65).

```
PROC MIXED;
  CLASS PERIOD SEQUENCE TIME SUBJ;
  MODEL  $\Delta\Delta\text{QTcF}$  = PERIOD SEQUENCE TIME BASELINE_QTcF;
  RANDOM SUBJECT (SEQUENCE);
  REPEATED TIME / SUBJ=SUBJ (PERIOD) TYPE=CS;
  LSMEANS TIME / ALPHA=0.025;
RUN;
```

In addition, using the above linear mixed effects model, least squares mean estimates of $\Delta\Delta\text{QTcF}$ and their one-sided 95% CIs for moxifloxacin will be obtained for the treatment effect at all post-dose timepoints without multiplicity correction and displayed graphically to demonstrate the time course of the moxifloxacin effect.

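### The rule for a negative zoliflodacin conclusion carries no moxifloxacin condition, and the plan does not say what is concluded if assay sensitivity is not shown

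*Protocol*

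**What the plan says.** Protocol 11.4.6.2 takes the upper one-sided 95% bounds for two doses at nine timepoints. Its rule is: "A negative effect of 2 g or 4 g zoliflodacin will be concluded if the maximum of the 18 one-sided 95% CI upper bound" is below 10 msec. ECG SAP 5.4 (Appendix 4 of the SAP) has the same rule: a negative effect "will be concluded if the maximum of the 18 one-sided 95% CI upper bounds is <10 msec". Protocol 11.1 defines a negative effect by the 10 msec criterion alone, and the primary outcome measure uses the same bound.

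Moxifloxacin is handled separately. Protocol 11.1 lists assay sensitivity as hypothesis b, beside the zoliflodacin hypothesis a. Protocol 11.4.6.4 introduces it with "Another secondary hypothesis is that a moderate increase in QTcF with administration of the positive control moxifloxacin 400 mg is detectable in this trial". The criterion is a lower bound above 5 msec at one or more of 1, 2, 3 and 4 h. ECG SAP 5.4 adds a Bonferroni correction and says that, if the criterion is met, "it will be concluded that the assay is sensitive to small increases in baseline QTcF duration". It gives no consequence if the criterion is not met.

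On purpose, Protocol 2.2.1 says: "The positive control (moxifloxacin) will serve to validate the sensitivity of the assay to detect small increases from baseline". Section 4.2 of the main SAP gives the same reason for including moxifloxacin.

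**The concern.** A positive control earns its place through what happens when it fails. Anything that damps measured QTcF change, such as poor extraction or insensitive reading, lowers the zoliflodacin upper bounds and makes the 10 msec criterion easier to meet. Moxifloxacin is the plan's in-trial check against that error, and the written rule does not use it. If the control failed, the prespecified rule would still return a negative conclusion, and any different interpretation would have to be chosen after the data were seen.

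**Working it through.** **Step 1: the text.** The two statements of the decision rule, the definition in Protocol 11.1 and the primary outcome measure all depend only on the zoliflodacin bounds. The assay-sensitivity rules in Protocol 11.4.6.4 and ECG SAP 5.4 depend only on moxifloxacin. No sentence in the protocol, main SAP or ECG SAP joins them.

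**Step 2: the plan's own power figure.** Inputs from Protocol 11.2 are SD 7 msec, effect 5 msec and 56 evaluable subjects, with stated power of at least 84%. The margin is 10 msec and the test is one-sided at 0.05.
- Taking 7 as the SD of the within-subject difference: SE = 7/√56 = 0.935 and power per interval is 99.99%. This does not match 84%.
- SE = 7 × √(2/56) = 1.323, equivalent to a difference SD of 7 × √2 = 9.9. Noncentral t with 55 df gives 98.16% per interval, and 0.9816⁹ = 84.6%. This matches for one dose with independent timepoints.
- All 18 bounds at SE 1.323, with assumed correlation 0.5 between timepoints and between arms, give 83.7%.

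Both SEs are carried forward.

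**Step 3: the rule when the control fails.** Zoliflodacin measures 5 msec and moxifloxacin 0-3 msec. Assay sensitivity is then met 0.0% of the time. The rule still returns a negative conclusion 83.6-83.7% of the time (SE 1.323) or 99.8% (SE 0.935).

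**Step 4: a damped recording.** Measured effect = capture fraction × true effect. Assumptions not in the documents are the capture fraction, correlation 0.5 throughout, flat effects over time and equal effects at both doses. I simulated 200,000 trials per scenario with 55 df. Negative means all 18 upper bounds are below 10. A moxifloxacin pass means any of four lower bounds, at one-sided 0.0125, is above 5.

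| Capture | True zoliflodacin → measured | Declared negative, SD 7 / SD 9.9 | True moxifloxacin → measured | Moxifloxacin passes, SD 7 / SD 9.9 |
|---|---|---|---|---|
| 40% | 15 → 6.0 | 95% / 54% | 10 → 4.0 | 0.1% / 0.4% |
| 40% | 15 → 6.0 | 95% / 54% | 15 → 6.0 | 28% / 17% |
| 60% | 12 → 7.2 | 52% / 14% | 12.5 → 7.5 | 90% / 64% |

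At 40% capture, requiring both criteria cuts the false negative conclusion from 95% to between under 0.1% and 23% (SD 7), and from 54% to at most 1.7% (SD 9.9). At 60% capture with SD 7 it only cuts 52% to 42%, because moxifloxacin usually still passes.

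**Step 5: a sound trial.** Protocol 2.2.1 expects a time-matched moxifloxacin effect of 10-15 msec. At 10 msec and SE 1.323, assay sensitivity is met about 99.5% of the time. At 12 msec or more, or at SE 0.935, it is met essentially always.

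**The case against.** The plan is silent about a failed control; it does not say it would stand behind a negative conclusion in that case. Timepoints, threshold and multiplicity correction for assay sensitivity are fixed in advance. The moxifloxacin time course is plotted, so a failure would be visible in the report. The trial declares that it follows ICH E14. Protocol 8.3.1 describes blinded central reading, one reader per subject and triplicate extraction, all of which make severe damping unlikely. At 10-15 msec the control should almost never fail. And because Protocol 11.1 defines a negative effect without moxifloxacin, building the condition into that term in one section would create a new inconsistency.

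Much of this stands. The low probability and the visibility of a failure lower the severity, and the point about the defined term decides the form of the fix. The general reference to E14 does not supply the missing condition, because the plan writes out its own decision rule and the definition it quotes contains only the 10 msec criterion. Visibility does not settle interpretation either: the rule would still call for a negative conclusion.

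A reader might also infer that the plan is likely to pass a harmful drug. The documents do not support that. The high false-negative rates arise only under an assumed, severe loss of capture, and they vary widely with the SE and the true moxifloxacin effect.

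**Conclusion.** The gap is real and lies in the decision rule itself: a negative conclusion follows from the 18 bounds alone, and nothing is prespecified for a failed control. It is a low-probability but consequential flaw, worth correcting but not one that invalidates the trial. A reader might infer that the sponsor intends to ignore moxifloxacin, or that the primary analysis is unsound. Neither follows: assay sensitivity is formally tested, and no estimate or interval would change.

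The finding rests on the text. The figures for a damped recording are illustrations that depend on the capture fraction and on the 0.5 correlations. The added condition protects mainly against severe damping and does much less at 60% capture or better.

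**What to change.** Keep the Protocol 11.1 definition of a negative effect for the 10 msec criterion. Add a trial-level rule to Protocol 11.4.6.2 and 11.4.6.4 and to ECG SAP 5.4, for example:

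*The trial is concluded negative for zoliflodacin only if the 18-bound criterion is met and assay sensitivity is demonstrated per 11.4.6.4. If the criterion is met but assay sensitivity is not demonstrated, the QTcF result is inconclusive.*

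No further alpha adjustment is needed: requiring both criteria cannot raise the chance of wrongly reaching the negative conclusion above that of the zoliflodacin criterion alone. No new data are needed.

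The cost is some power to reach the trial-level conclusion. At a zoliflodacin effect of 5 msec, SE 1.323 and a 10 msec moxifloxacin effect, power goes from 83.8% to 83.4%; across 10-15 msec the loss is at most about 0.5 points. It grows if moxifloxacin shows less: at 8 msec power falls from 83.6% to 65.3% (SE 1.323), or from 99.9% to 97.5% (SE 0.935). The sample-size section should say whether its power refers to the 18-bound criterion or to the trial-level conclusion.

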11.4.6.3 Secondary Analyses: Non-QTc Intervals

Non-QTc intervals (PR, QRS, and RR intervals) and HR (estimated from measurement of RR intervals) will be tabulated at each timepoint for each treatment group and the mean \pm SD, median, 95% CI, minimum, and maximum values will be shown. Comparisons among treatment groups will be done using linear mixed effects models.

Categorical analysis of PR, QRS, and RR intervals will also be performed. The following criteria will be used to specify noteworthy non-QTc intervals (PR, QRS, and RR intervals) and HR (derived from RR intervals) and the number of subjects and number of timepoints will be tabulated for each treatment group and may be compared statistically:

- PR change-from-baseline $>25\%$ resulting in PR >200 msec
- QRS change-from-baseline $>25\%$ resulting in QRS >120 msec
- HR change-from-baseline $>25\%$ decrease resulting in HR <50 bpm
- HR change-from-baseline $>25\%$ increase resulting in HR >100 bpm

11.4.6.4 Assay Sensitivity

Another secondary hypothesis is that a moderate increase in QTcF with administration of the positive control moxifloxacin 400 mg is detectable in this trial.

The model as described in the primary analyses will be repeated with the moxifloxacin treatment for assay sensitivity evaluation. The 1, 2, 3, and 4 h timepoints will be evaluated for assay sensitivity. Type I error (familywise error rate) will be controlled at an overall level of 5% by using a prespecified multiplicity adjustment. Assay sensitivity will be demonstrated if the lower bound of one-sided 95% CI (bounds will vary based on multiplicity adjustment) for treatment effect on $\Delta\Delta\text{QTcF}$ in at least one timepoint is >5 msec. In addition, two-sided 90% CIs will be obtained for the treatment effect on $\Delta\Delta\text{QTcF}$ at every timepoint and displayed graphically.

11.4.6.5 Categorical Analyses

QTcF intervals will be categorized and tabulated for each treatment. The following criteria will be used to specify noteworthy QTcF intervals:

- QTcF >450 msec
- QTcF >480 msec

- QTcF >500 msec
- QTcF increase ≥ 30 msec from baseline
- QTcF increase ≥ 60 msec from baseline

The number and percent of subjects in each category will be calculated. Comparisons across treatments may be conducted if sufficient counts are observed.

11.4.6.6 Cardiac Abnormalities:

The morphological waveform analysis of the ECG data for TQT evaluations at each timepoint will be utilized for the summary of new onset cardiac abnormalities for each treatment. Results will be summarized in frequency tables with counts and percentages for both number of subjects and number of timepoints.

11.4.7 Concentration-QTcF Modeling

Concentration-QTcF modeling will be utilized to characterize the exposure-QTcF relationship for zoliflodacin.^{25,26} Initially, linear or non-linear mixed-effect models will be fit to $\Delta\Delta$ QTcF values for only the zoliflodacin arms. More complex models will be employed if simpler models provide inadequate model fit. Hysteresis effects will be examined and may be utilized to characterize the delayed effects if observed. Estimates of the mean prolongation at the geometric mean zoliflodacin C_{max} for the zoliflodacin 2-g and 4-g doses will be made from the final exposure response model with corresponding two-sided 90% CIs.

Detailed analysis plans will be documented in the SAP. Results of the concentration-QTcF evaluations will be reported in the CSR.

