10.3. Definition and Estimation of Individual NCA PK Parameters

PK parameters will be estimated through a NCA using Phoenix[®] WinNonlin[®] version 8.0 or later (Pharsight Corporation, Cary, NC). Actual post-dose time will be used for the estimation of PK parameters instead of nominal time. Individual PK parameter estimates will be listed ([Listing 28](#)).

Phoenix WinNonlin[®] NCA will use the following settings to compute parameters from plasma PK data:

- Linear Up Log Down calculation method
- Uniform weighting
- Oral dosing
- Lambda Z Acceptance Criteria
 - $R_{sq_adjusted} \geq 0.80$
 - $Span \geq 2.5$ half-lives
 - Includes at least 3 timepoints after T_{max}

C_{max}

C_{max} is defined as the maximum observed drug concentration observed in plasma over all PK sample concentrations. It will be obtained from the **C_{max}** parameter calculated by WinNonlin[®]. If there is no measurable concentration in the subject's PK profile, then C_{max} will be missing for that subject. C_{max} will be reported in units of ng/mL.

T_{max}

Time of maximum plasma concentration (T_{max}) is defined as the time at which the C_{max} occurs. It will be obtained from the **T_{max}** parameter calculated by WinNonlin[®]. If there is no measurable C_{max} in the subject's PK profile, then T_{max} will be missing for that subject. T_{max} will be reported in units of h.

K_e

The terminal phase elimination rate constant (K_e) is defined as the first-order rate constant describing the rate of decrease of drug concentration in the terminal phase (defined as the terminal region of the PK curve where drug concentration follows first-order elimination kinetics). K_e will be computed as the slope of a terminal region consisting of ≥ 3 successive points in the plot of log-transformed concentration data versus time. K_e will be estimated using uniform weighting.

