		21. Section 5.5 deleted 'its metabolites (if available)'	As per review comments – no metabolites data available

		22. Added section numbering to methods of Concentration QTcF analysis	As per review comments
		23. Test of linearity section – Corrected Δ QTcF to $\Delta\Delta$ QTcF	As per reviewer’s observation
Final	18SEP2018	Accepted minor edit comments throughout the document	As per Sponsor’s comments
		Added reference of the scientific white paper	As per Sponsor’s comments
		Modified the SAS code in section 5.4	As per IQVIA reviewer’s input

Abbreviations and Definitions

Abbreviation or specialist term	Explanation
AE	Adverse event
AIC	Akaike Information Criterion
ANCOVA	Analysis of covariance
AUC	Area under the curve
AV	Atrioventricular
β_2	Model-predicted estimates of slope
bpm	Beats per minute
CI	Confidence interval
C_{max}	Maximum plasma concentration
CS	Compound symmetry
CSS	Cardiac Safety Services, IQVIA
CTU	Clinical trial unit
CV	Coefficient of variation
DDFM	Denominator degrees of freedom method
DMID	Division of Microbiology and Infectious Diseases
ECG	Electrocardiogram
E_{max}	Nonlinear model frequently used in dose–response analyses
ET	Early termination
g	Gram
h	Hour
HR	Heart rate
Hz	Hertz
ICH	International Council for Harmonization
LCL	Lower confidence limit
LOESS	Locally-weighted scatterplot smoothing
LS	Least square

Abbreviation or specialist term	Explanation
LVH	Left ventricular hypertrophy
Max	Maximum
mg	Milligram
MI	Myocardial infarction
Min	Minimum
msec	Milliseconds
N	Number of observations
PD	Pharmacodynamics
PK	Pharmacokinetics
PO	Oral
PR interval	Interval from onset of P-wave to the onset of the QRS complex
QRS	Duration from the start of the Q-wave to the end of the S-wave
QT interval	Interval from onset of the Q-wave to the end of the T-wave
QTc	Corrected QT interval
QTcB	QT interval corrected by Bazett's formula
QTcF	QT interval corrected by Fridericia's formula
Δ QTcF	Change-from-baseline QTcF value
$\Delta\Delta$ QTcF	Placebo-corrected change from baseline QTcF value
RR	Interval from the peak of the R wave of a QRS complex to the peak of the R wave of the next QRS complex
SAE	Serious adverse event
SAP	Statistical analysis plan
SD	Standard deviation
SE	Standard error
TQT	Thorough QT/QTc
T _{max}	Time to maximum plasma concentration
T-wave	ECG wave indicative of ventricular repolarization

Abbreviation or specialist term	Explanation
UCL	Upper confidence limit
UN	Unstructured covariance
VS	Vital signs

1. Introduction

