5.5.1. Hysteresis effect check

To assess if there is a time dependency (a hysteresis effect) between zoliflodacin concentration and $\Delta\Delta\text{QTcF}$ visually, zoliflodacin concentration and $\Delta\Delta\text{QTcF}$ will be plotted vs. timepoint in a single plot and visually inspected for a difference between T_{\max} for concentration and T_{\max} for $\Delta\Delta\text{QTcF}$. In addition, a scatter plot of mean $\Delta\Delta\text{QTcF}$ and mean plasma zoliflodacin concentration values from all subjects at each timepoint will be plotted using different colors and symbols for the 2 g and 4 g dose groups and the points connected in temporal sequence. If there is a unique value of $\Delta\Delta\text{QTcF}$ for each value of concentration, even as time evolves, the plot suggests no hysteresis. If plot shows that the value of $\Delta\Delta\text{QTcF}$ for a given value of concentration differs as time evolves, and the values of $\Delta\Delta\text{QTcF}$ observed before T_{\max} consistently differ from the values observed at a similar concentration at a timepoint after T_{\max} this would suggest presence of hysteresis (Refer to DMID 16-0110_ECG_Figure shells: Figures 66 and 67). If hysteresis is present, a PK model with an additional effect compartment will be used.⁴ In this case, the concentration in the effect compartment (C_e) will be calculated and used in the model instead of the original concentration.

5.5.2. Testing for linearity:

A potential non-linear relationship between zoliflodacin concentration and $\Delta\Delta\text{QTcF}$ will be assessed visually and statistically (Refer to DMID 16-0110_ECG_Table shells: Table 12 and 13; DMID 16-0110_ECG_Figure shells: Figure 69).

In the visual approach, a scatter plot of $\Delta\Delta\text{QTcF}$ versus zoliflodacin plasma concentration for all timepoints will be generated and the locally weighted scatterplot smoothing (LOESS) and its one-sided 95% CI will be plotted and inspected for nonlinearity.³ A PK-PD model with $\Delta\Delta\text{QTcF}$ as the dependent variable and zoliflodacin concentration and quadratic term of zoliflodacin concentration as independent variables will be performed using PROC MIXED with slope of concentration and quadratic term of concentration and intercept as subject-specific random effects.⁴

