If there is no clear indication of nonlinearity based on visual inspection of the $\Delta\Delta\text{QTcF}$ vs. concentration plot, or the quadratic term for concentration is non-significant at a two-sided alpha level of 0.05, a linear mixed effects modeling approach will be used.⁴ If there is an indication of a nonlinear relationship, a nonlinear mixed effect modeling approach will be examined. Akaike Information Criterion (AIC) of linear and different nonlinear mixed effect models including log-linear and E_{\max} will be calculated. The model with the least AIC will be considered as the final model for concentration-effect modelling.⁴

5.5.3. Model selection:

The selection of the PK-PD model for evaluating zoliflodacin concentration and $\Delta\Delta\text{QTcF}$ will follow the assessment of hysteresis and non-linearity.⁵ If there is no evidence of hysteresis and no indication of nonlinearity, linear mixed effects modeling approach will be used to quantify the relationship between zoliflodacin plasma concentration and $\Delta\Delta\text{QTcF}$.

The model will include $\Delta\Delta\text{QTcF}$ as the dependent variable, with zoliflodacin concentration as fixed effects and intercept and slope as subject-specific random effects. Unstructured covariance (UN) structures will be used and denominator degrees of freedom method (DDFM) will be set to Kenward-Roger.⁶ The subject-specific slope random effect will be dropped from the model or concentration values will be rescaled if the model fails to converge.

Model-predicted parameter estimates (model-predicted estimates of slope $\{\beta_2\}$, SE of β_2 , p-values (for slope $\{\beta_2\}$ and overall model fit), predicted $\Delta\Delta\text{QTcF}$ and its upper bound of the one-sided 95% confidence limit at geometric mean C_{\max} [separately for zoliflodacin 2 g PO and zoliflodacin 4 g PO]) will be calculated (Refer to DMID 16-0110_ECG_Table shells: Tables 14 and 15; DMID 16-0110_ECG_Listing shells: Listings 16 and 17; DMID 16-0110_ECG_Figure shells: Figure 70).

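### If hysteresis leads to an effect-compartment model, the predicted ΔΔQTcF is still tied to plasma Cmax, which taken literally overstates a positive concentration effect

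*Protocol*

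**What the plan says.** Four places bear on this point.

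- **Protocol 11.4.7.** Hysteresis comes first: "Hysteresis effects will be examined and may be utilized to characterize the delayed effects if observed". The readout follows. The estimates at geometric mean Cmax "for the zoliflodacin 2-g and 4-g doses will be made from the final exposure response model", with two-sided 90% confidence intervals. One readout is named for whichever model turns out to be final.
- **ECG SAP 5.5.1** (Appendix 4 of the SAP) is firmer: "If hysteresis is present, a PK model with an additional effect compartment will be used". In that case Ce "will be calculated and used in the model instead of the original concentration".
- **ECG SAP 5.5.3** sets out one model in detail: "If there is no evidence of hysteresis and no indication of nonlinearity, linear mixed effects modeling approach will be used". It then lists the outputs, including predicted ΔΔQTcF and its "upper bound of the one-sided 95% confidence limit at geometric mean" Cmax, separately for each dose. A one-sided 95% upper limit is the same number as the upper end of the protocol's two-sided 90% interval.
- **Definition of Cmax.** The ECG SAP abbreviation list has "Maximum plasma concentration". The main SAP, section 10.3, says Cmax "is defined as the maximum observed drug concentration observed in plasma over all PK sample concentrations". Neither document defines a peak effect-compartment concentration (Ce,max).

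**The concern.** In the effect-compartment model the slope is in msec per unit of Ce. Ce lags behind plasma and is smoothed, so after a single dose its peak is lower than plasma Cmax. Multiplying a per-Ce slope by plasma Cmax gives the effect at an effect-site concentration that a typical subject does not reach. The readout rule is right for a direct model and wrong for this one.

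The predicted ΔΔQTcF at each dose, with its bound, is the main result of the concentration-QTcF analysis and goes into the clinical study report. If hysteresis were found and the slope were positive, that result would be inflated. It could then sit above the peak seen in the by-timepoint analysis of the same data and raise a signal that the observed means do not show.

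**Working it through.** **Plan's own figure.** The documents give no figure for this readout. The only stated power (at least 84%) belongs to the primary by-timepoint test, and this point does not depend on it.

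**Inputs.** Zoliflodacin half-life of about 6 h (protocol 2.2.1; SAP 4.2), so ke = ln 2 / 6 = 0.1155 per h. Tmax is redacted in the protocol, and neither an absorption rate nor an equilibration rate is given. I therefore *assume* ka of 0.5 to 2 per h and an equilibration half-life of 0.5 to 4 h.

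**Formulas.** One-compartment oral profile, unit scale: Cp(t) = ka/(ka − ke) × (exp(−ke·t) − exp(−ka·t)). Effect compartment: dCe/dt = ke0 × (Cp − Ce), with ke0 = ln 2 / equilibration half-life. When Ce peaks, dCe/dt = 0, so Ce,max equals Cp at that later time. That is on the falling limb, so Ce,max is below Cmax.

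**Worked case, ka = 1 per h, equilibration half-life 1 h.**

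- Plasma peak at 2.44 h: Cmax = 0.754.
- Ce peak at 4.46 h: Ce,max = 0.662.
- Ratio: 0.662 / 0.754 = 0.88.
- Overstatement: 1/0.88 − 1 = 14%.

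**Range, ka = 1 per h.** Reading = true peak effect divided by the ratio, for a linear model with zero intercept.

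| Equilibration half-life | Ce,max/Cmax | Overstatement | True 5 msec reads | True 8 msec reads |
|---|---|---|---|---|
| 0.5 h | 0.96 | 4% | 5.2 | 8.3 |
| 1 h | 0.88 | 14% | 5.7 | 9.1 |
| 2 h | 0.75 | 34% | 6.7 | 10.7 |
| 4 h | 0.58 | 72% | 8.6 | 13.7 |

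Over the whole assumed grid the ratio runs from 0.98 (ka 0.5, 0.5 h) to 0.53 (ka 2, 4 h), an overstatement of 2% to 89%. Any fixed intercept would not be scaled, so the percentages apply to the concentration-dependent part of the prediction.

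**Direction and bound.** I simulated a mixed model of ΔΔQTcF on Ce: 56 subjects, both doses, nine timepoints, random intercept, Tmax 2.5 h, equilibration half-life 1 h, Ce taken as known, averages over 20 data sets. The table gives prediction / one-sided 95% upper bound at 4 g, in msec.

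| True 4-g peak | Read at geometric mean Ce,max | Read at geometric mean plasma Cmax |
|---|---|---|
| 8 | 7.6 / 8.5 | 8.7 / 9.7 |
| 5 | 4.7 / 5.6 | 5.5 / 6.4 |
| 0 | 0.1 / 1.0 | 0.1 / 1.0 |
| −5 | −4.9 / −4.0 | −5.6 / −4.6 |

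With a positive slope, prediction and bound are both too high. At zero slope the bound moves by under 0.1 msec. With a negative slope both are too low.

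**The case against.** **The documents do not expressly order this readout for a Ce model.** In ECG SAP 5.5.3 the outputs come straight after the model for no hysteresis and no nonlinearity, where plasma Cmax is correct. An analyst could also carry the substitution of Ce through to the prediction. The table and listing shells cited there were not available. This stands in part: a reader might infer that the SAP prescribes plasma Cmax for a Ce-based slope, and it does not say so. The conflict rests mainly on the protocol's reference to the final model, which directly follows its sentence on hysteresis. If the branch is instead treated as silent, the analyst must choose after seeing the data. One further candidate, Ce at the time of plasma Tmax, errs the other way: over assumed Tmax of 1.5 to 4 h and equilibration of 0.25 to 4 h it is 0.34 to 0.995 of Ce,max.

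**The size is driven by assumptions.** This stands. The range runs from trivial to large, and the documents cannot narrow it. On the other side, the branch opens only if a delay is visible, and small delays are hard to see on this sampling grid. In the worked case a 1 h equilibration half-life moves the peak by about 2 h (2.44 to 4.46 h) and costs 14%.

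**The 8 msec illustration favours crossing 10 msec.** Fair. The plan's sample-size effect is 5 msec. Even at 89% that reads as 5 × 1.89 = 9.5 msec as a point prediction, and only the bound could pass 10.

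**The error would be visible.** ECG SAP 5.5.1 and 5.6 plot ΔΔQTcF and concentration over time, and 5.5.3 checks observed means by concentration decile. A prediction well above every observed mean should stand out. That helps detection, but does not say which number to report.

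**Conclusion.** The inconsistency is real, and limited. If the effect-compartment model becomes final, the protocol's readout at geometric mean Cmax does not match the covariate that the ECG SAP puts into the model. Taken literally, a positive effect is overstated by about 2% to 89%. That range rests on the stated 6 h half-life, a one-compartment profile with a first-order effect compartment, a linear model with zero intercept, and the assumed ka and equilibration half-lives.

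A reader might infer that the predicted effect will always be biased upward. It will not: a flat slope leaves it essentially unchanged, a negative slope reverses the error, and fast equilibration makes it small. A reader might also infer that the trial's conclusion is at risk. It is not. The negative-effect conclusion rests on the 18 by-timepoint upper bounds (protocol 11.4.6.2; ECG SAP 5.4). The concentration-QTcF analysis is secondary and has no threshold attached. For a prolonging drug the error is on the cautious side. It remains worth correcting, because the prediction is a reported result and the choice of readout should be settled before the data are seen.

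**What to change.** Add one sentence to protocol 11.4.7 and the same to ECG SAP 5.5.3, to this effect: when the final model is direct, ΔΔQTcF and its confidence bound are predicted at the geometric mean plasma Cmax; when it is the effect-compartment model, they are predicted at the geometric mean of the subjects' model-derived peak effect-compartment concentration (Ce,max); in both cases separately for 2 g and 4 g. Define Ce,max in the ECG SAP alongside Cmax.

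The cost is a wording change in two documents. Ce is already to be calculated under ECG SAP 5.5.1, so no new data, samples or procedures are needed, and the primary analysis is untouched.
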